## II. INTRODUCTION

Toothbrushes with tapered bristles were designed to clean plaque accumulated interdental area effectively. *In vitro* studies showed that the effectiveness in artificial plaque reduction is greater than that of the conventional toothbrushes with end rounded bristles. However, clinical studies in dental plaque and gingivitis have not showed consistent result in the superiority comparing to conventional toothbrushes. The purpose of this cross-over clinical research is to evaluate the cleaning efficacy of toothbrushes tufted with two types of tapered bristles and end rounded bristles in removal of interdental plaque with clinical measurement (Plaque Index) and objective measurement (digitally measured plaque area). This Proof of Concept study will demonstrate the influence by a type of processing bristles on removal of interdental plaque and determine an agreement between the different evaluation methods.

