## III. STUDY OBJECTIVES

The primary objective of this study is to evaluate and compare toothbrushes with three different bristle types in the reduction of plaque index (**PI**) for interdental area and digitally measured interdental plaque area after one-time brushing.

Secondary objectives are to evaluate toothbrushes with three different bristle types in the changes of PI, digitally measured interdental plaque area and gingival abrasion one week after using the toothbrushes, and to assess an agreement between the different evaluation methods (**PI** and a plaque area by image analysis)

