## IV. STUDY GROUPS

Three different bristles will be tufted into the same tuft pattern. All toothbrush head and handle are identical (Sonic TB without turning on the sonic vibration). The study samples will be provided by sponsor. The bristle dimensions (height, base diameter of filament) will be same. The difference of three toothbrushes is a type of processing bristles.

- A: Tapered bristles (double tapered J-hook)
- B: Tapered bristles (single tapered J-hook)
- C: End rounded bristles

Table 1. Physical characteristics of the bristles in all test groups

	Product A	Product B	Product C
Name	Double tapered J-hook (OTJ)	Single tapered J-hook (STJ)	End rounded (Control)

Version 061020

Individual filament heights in all tufts	10 and 13 mm	10 and 13 mm	13 and 13 mm
Tall filament end	Chemically tapered	Chemically tapered	Rounded
Short filament end	Chemically tapered	Rounded	Rounded
Filament's base diameter, milli inch (mm)	7 (0.18)	7 (0.18)	7 (0.18)
Filament material	PBT**	PBT**	Nylon

\*Pending, to check with supplier, \*\* Polybutylene terephthalate

[figure not shown]

Figure 1. Toothbrush head schematic showing tuft patterns (circles) used in all test groups

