## VI. SUBJECT POPULATION

### **Number of Subjects**

A total number of 10 subjects will be enrolled. Volunteers must read and sign the Informed Consent Form after the nature of the study has been fully explained.

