## **XV. EFFICACY**

### **Primary Outcome Variables**

The primary outcome variables to be assessed are:

- 1) the reduction of plaque index (Navy PI) for interdental area after one-time brushing in a whole mouth.
- 2) the reduction of digitally measured interdental plaque area on non-molar teeth, facial/buccal aspect after one-time brushing by image analysis.

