## XVI. STATISTICAL ANALYSIS AND DATA MANAGEMENT

Since this study is a Proof of Concept study, the sample size calculation was not performed.

Descriptive statistics for all subjects will be performed for background and demographic variables. Continuous variables are expressed as frequencies (n), mean +/- SD and categorical variables are expressed as frequencies (n) and percentages (%).

Student *t* test or Wilcoxon *rank sum* test where appropriate, will be used to compare among different bristles. For intragroup changes of endpoints before/after one-time brushing or use for one-week, paired *t* test or Wilcoxon signed rank test will be used where appropriate. Spearman Rank Order Correlation was used to analyze correlations between the variables.

Safety parameters will include oral soft and hard tissues and subjective reports as well as any AEs. The analysis will include all observed effects which initially occurred or worsened following treatment. Any adverse effects will be summarized classified according to their intensity (mild, moderate, or severe) and relationship (definitely related, probably related, possibly related, probably not related or definitely not related) to study product.

All statistical tests will be conducted using Minitab 18.

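### Every subject uses all three brushes, but the brushes are compared with two-sample tests, so the primary comparison ignores the cross-over and mainly loses power

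*Combined protocol and SAP*

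**What the plan says.** Section VII (Study Design Overview) describes a three-period cross-over with sequences A-B-C, B-C-A and C-A-B. Each sequence contains every brush, so each subject contributes one result per brush. On numbers, Section VI says "A total number of 10 subjects will be enrolled".

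Section III sets the primary objective, to "evaluate and compare toothbrushes with three different bristle types in the reduction of plaque index" and in digitally measured interdental plaque area. Section XV lists both measures under "The primary outcome variables to be assessed are", without ranking them.

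Section XVI assigns two families of test. For brush against brush, Student t or a rank sum "test where appropriate, will be used to compare among different bristles". The paired t and signed rank tests come in the next sentence, which begins "For intragroup changes of endpoints before/after one-time brushing or use for one-week". There is no overall three-brush test, period term, alpha level or multiplicity rule. On size it says only "Since this study is a Proof of Concept study, the sample size calculation was not performed".

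The pairs to be tested are not listed. Section III supports A-B, A-C and B-C. Table 1 in Section IV labels product C "End rounded (Control)", which could support A-C and B-C only.

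**The concern.** A two-sample test takes the variance of a mean difference to be the sum of two independent variances. In this design the same people supply both means, so differences between people cancel from the comparison. The planned test leaves them in its error term. That gives up the main advantage of a cross-over in a study with only 10 subjects.

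Two things follow. If a person's results on different brushes are positively correlated, a real brush difference is more likely to be missed, and a null result may reflect the test rather than the bristles. In addition, the true error rate behind a nominal p-value depends on a correlation that the documents do not give. Section II states an inferential aim ("This Proof of Concept study will demonstrate the influence by a type of processing bristles on removal of interdental plaque"), so the between-brush test carries the study's main message.

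**Working it through.** The plan has no power or error figure to reproduce. The check compares the planned test with a within-subject test on the same data.

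**Inputs from the documents:** n = 10 subjects, each on 3 brushes, giving 3 pairs per outcome, with two-sample tests between brushes. Ten completers is the best case, because Section XIV does not replace withdrawals.

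**Assumptions, not in the documents:** 5% two-sided per test; true difference δ = 0.8 SD with total SD σ = 1; normal data, equal variances and no period or carry-over effect; within-subject correlation ρ from 0 to 0.7.

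**Step 1: the mismatch.** The planned t test has 2n − 2 = 18 df and takes the variance of a mean difference to be 2σ²/n = 0.20. In the cross-over it is 2σ²(1 − ρ)/n, which is 0.20 at ρ = 0, 0.10 at 0.5 and 0.06 at 0.7.

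**Step 2: paired power.** The noncentrality is δ√n / √(2(1 − ρ)) with n − 1 = 9 df.
- ρ = 0: 2.530/1.414 = 1.79, power 36%
- ρ = 0.3: 2.530/1.183 = 2.14, power 48%
- ρ = 0.5: 2.530/1.000 = 2.53, power 62%
- ρ = 0.7: 2.530/0.775 = 3.27, power 83%

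**Step 3: the planned tests, by simulation** (200,000 trials per setting for t, 20,000 for rank sum). At ρ = 0 the noncentral t gives 39.5% single-pair power, which agrees.

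| ρ | Any false difference, 3 planned t tests, one outcome | Planned t, single-pair power | Rank sum, single-pair power | Paired t, single-pair power |
|---|---|---|---|---|
| 0 | 12.2% | 39.5% | 35% | 36% |
| 0.3 | 5.9% | 37.9% | not run | 48% |
| 0.5 | 2.6% | 36.7% | 32% | 62% |
| 0.7 | 0.6% | 35.1% | 31% | 83% |

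The second column concerns any of three pairs; the power columns concern one pair. At ρ = 0.4 the false-difference chance is 4.0%, so it passes below 5% near ρ = 0.35. It continues to fall, to 0.2% at 0.8 and 0.01% at 0.9. If only A-C and B-C are tested it is 9%, 4%, 1.8% and 0.4% at ρ = 0, 0.3, 0.5 and 0.7.

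**Step 4: what pairing alone leaves.** Three unadjusted within-subject contrasts give about 12-13% false differences per outcome at every ρ. The overall 2-df F test holds 5%.

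**Step 5: period.** Brushing instruction is repeated at Visits 2, 4 and 6 (Table 2), so a learning trend is plausible. Take an illustrative trend of 0.4 SD per period, 4/3/3 allocation, and A differing by 0.8 SD from B = C. With contrasts read only after a significant period-adjusted overall test, A-C power at ρ = 0.7 is 53% for simple paired contrasts and 82% for the model's period-adjusted contrasts. At ρ = 0.5 it is 37% and 57%.

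**The case against.** **The wording is flexible.** Student t might be read loosely, Section XVI allows a choice where appropriate, and Section XV permits further exploratory analysis. None of this cures the mismatch. Rank sum is set against signed rank in consecutive sentences, the choice offered is between two independent-samples tests, and the exploratory clause specifies no analysis.

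**The planned tests are conservative.** This holds above a correlation of about 0.35, and it limits the point. A reader might infer that the plan inflates false positives. The documents do not support that as a general statement: inflation over three pairs arises only at low correlation, and no correlation is given. At the positive correlations a cross-over is meant to exploit, the cost is lost power. Nor is 0.6% a floor.

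**This is a proof-of-concept study.** That explains the absent sample size calculation, not a test that ignores the design. It does bear on multiplicity. A reader might infer that the lack of an overall test or of a rule across the two primary outcomes is a failure of error control. With 10 subjects and no stated alpha, success rule or confirmatory claim, gating and cross-outcome control are discretionary.

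**Intervals.** A reader might also infer that the plan's confidence intervals are too wide. Section XVI states none, so there is nothing of that kind to correct.

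**The remedy can lose power.** True at low correlation; see the cost below.

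**Conclusion.** The point stands as a mismatch between design and analysis that should be corrected before the data are analysed. On the assumptions listed, the planned t test has single-pair power for 0.8 SD of about 37% at correlation 0.5 and 35% at 0.7 (rank sum about 32% and 31%), so the shortfall against a paired t test is roughly 25 and 48 percentage points (62 − 37 and 83 − 35). Lost power is the main harm. Miscalibrated p-values are the secondary one, running in either direction according to the correlation.

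The mismatch is plain from the text. The sizes depend on inputs the documents do not supply (alpha, effect size, correlation) and on normality, 10 completers and no period effect. They show the scale of the loss and do not predict this study's power.

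**What to change.** In Section XVI, replace the two-sample between-brush tests with the following.

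- For each primary outcome, fit a within-subject model with subject as block and terms for brush and period. Report the overall 2-df brush test.
- Give A-B, A-C and B-C as period-adjusted contrasts from that model with 95% CIs, whatever the overall result.
- Use Friedman and signed-rank tests if normality is untenable, noting that in their simple form they do not adjust for period.
- If error variances clearly differ between brushes, allow for that in the contrasts. As an illustration, with error SDs of 0.5:1:1 and only A truly different, pooled-error contrasts after the overall test gave a false B-C difference in 8.4-8.7% of trials, against 4.8-5.1% with separate paired errors.
- State the alpha level. Either read the pairwise contrasts only after a significant overall test, or label them exploratory.
- State that the two primary outcomes are read separately and are not confirmatory.

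The cost is a few sentences, with no new data or visits. Gating costs some power: with simple paired contrasts and no period effect, A-C power falls from 83% to 75-80% at correlation 0.7 and from 62% to 51-55% at 0.5, still above the planned test. Below a correlation of about 0.3 the gated analysis can have less power than the planned test (about 27-30% against 40% at correlation 0), but there the planned tests carry about 12% false differences per outcome.

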## **VII. STUDY DESIGN OVERVIEW**

This cross-over group, examiner blinded, randomized, single center study will enroll subjects to target 10 subjects completing the study. Subjects will visit the clinical site 7 times including screening/enrollment visit. Subjects will be instructed to refrain from regular oral hygiene regimen for 24 hours and from eating for four hours before each appointment. The study examiner and staff will screen for subjects that meet the enrollment criteria. Subjects will be randomly assigned to one of three treatment groups. The study staff responsible for random assignments will be blinded to the product treatments.

- Group 1: A -> B -> C
- Group 2: B -> C ->A
- Group 3: C ->A-> B

After distribution of an assigned test toothbrush, subjects will receive a basic brushing instruction for Bass method by a study staff but without actual brushing. Subjects will perform toothbrushing using the assigned product for 2 minutes under supervision. Plaque Index (Navy PI), Gingival Abrasion Score and standardized digital dental photos will be taken before/after the one-time brushing.

Subjects will use the assigned toothbrush for a week until the next visit for evaluation. At the visit, the used toothbrush shall be returned to the study staff to avoid mixing up with next test product. PI and Gingival Abrasion Score will be recorded, and the standardized digital dental photos will be taken. After one week of wash-out period, subjects will return to the clinical site to start the next test product. The study schedule is showed in Table 2. Subjects will be instructed to keep a diary given by the study staff at Visit 1 throughout the study. Adverse experiences will be noted and recorded during the study.

Version 061020

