### **Subject Withdrawal**

Subjects are free to withdraw at any time during the clinical trial. Subjects may also be withdrawn from the study at any time at the discretion of the Investigator. All subject withdrawals will be documented in the study file. Where possible, the reason for the withdrawal will be documented. Any withdrawals as the result of an adverse event will be followed-up at the discretion of the Study Investigator. Withdrawn subjects will not be replaced.

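### Brush comparisons are planned as tests only; with 10 subjects the main result should be within-subject brush differences with 95% confidence intervals

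*Combined protocol and SAP*

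**What the plan says.** Section XVI is the whole statistical plan. For differences between brushes it says that a Student t test or a Wilcoxon rank sum test "will be used to compare among different bristles". For changes within a brush it names a paired t test or a signed rank test. It then says how continuous variables are summarised (n, mean and SD), directly after a sentence about background and demographic variables. No section plans an estimated brush difference or a confidence interval, or states a significance level.

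On size, section VI says "A total number of 10 subjects will be enrolled", section VII says the study "will enroll subjects to target 10 subjects completing the study", and section XIV says "Withdrawn subjects will not be replaced". Section XVI adds: "Since this study is a Proof of Concept study, the sample size calculation was not performed".

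The Introduction gives the purpose: "This Proof of Concept study will demonstrate the influence by a type of processing bristles on removal of interdental plaque". Section VII describes a three-period cross-over with sequences ABC, BCA and CAB, so each completing subject uses every brush.

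**The concern.** The stated purpose is a question of effect size: how much does the way the bristle is processed change interdental plaque removal? A test answers only whether a difference of zero can be rejected. In a study of 10 subjects with no size calculation, a non-significant test may reflect no effect or a large effect measured imprecisely, and the p value does not tell these apart. An interval shows directly which differences remain plausible. That is the information needed to decide whether a larger trial is worthwhile and how large it should be. If the plan is followed as written, the report need not contain it.

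**Working it through.** The plan states no power, SD, effect size or significance level, so there is no figure to reproduce. The check works in SD units.

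**Inputs**
- n = 10, each subject due to use all three brushes (sections VI and VII).
- Two-sided 5% tests and 95% intervals: assumed.
- Correlation r between a subject's reductions with two brushes: not given, so 0.3, 0.5 and 0.7 are shown.
- Student t is read as the two-sample test, because section XVI names the paired t test separately for changes within a brush.

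**1. Width of a paired interval**
- Half-width = t(0.975, n-1) / sqrt(n), in SD of the within-subject difference.
- n = 10: 2.262 / 3.162 = 0.715.
- A result exactly at p = 0.05 has an interval from 0 to 2 x 0.715 = 1.43 SD.
- An observed difference of 0.70 SD is non-significant, with an interval from 0.70 - 0.715 = -0.015 to 0.70 + 0.715 = 1.415 SD.
- If two subjects withdraw, n = 8 gives a half-width of 0.84 SD.

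**2. Power of a paired t test (noncentral t, 9 df, noncentrality d x sqrt(10))**

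| True difference (SD of within-subject difference) | Power | Non-significant |
|---|---|---|
| 0.5 | 29% | 71% |
| 0.8 | 62% | 38% |
| 1.0 | 80% | 20% |

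**3. The two-sample t test as written (18 df, 10 observations per brush, treated as independent)**
- Half-width = t(0.975, 18) x sqrt(2/10) = 2.101 x 0.447 = 0.94 single-period SD.
- Nominal power is 19%, 40% and 56% for true differences of 0.5, 0.8 and 1.0 single-period SD.
- An interval printed with this test would ignore the pairing.

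**4. Why means and SDs by brush are not enough**
- With equal per-brush SD s, the SD of the difference is s x sqrt(2(1 - r)).
- The paired half-width is then 0.715 x sqrt(2(1 - r)) in units of s: 0.85 at r = 0.3, 0.72 at r = 0.5 and 0.55 at r = 0.7.
- The same table of per-brush SDs is thus compatible with half-widths that differ by a factor of 0.85 / 0.55, about 1.5. A reader cannot recover the interval from it.

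**5. A model that uses all three periods**
- Error df with subject, brush and period terms: 30 - 1 - 9 - 2 - 2 = 16.
- Half-width = 2.120 / sqrt(10) = 0.670 SD of the within-subject difference, assuming the same error variance for every brush.
- Ten subjects cannot divide equally among three sequences. A 4/3/3 split gives 0.674.

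**The case against.** The strongest reply is that this is an openly labelled proof-of-concept study. Section XVI states no success criterion or decision rule, the sentence on means and SDs can be read as covering outcomes by brush, and section XV allows further exploratory analysis. On that reading, point estimates by brush are planned, and a difference follows by subtraction when all subjects complete. Intervals would also display the limits of a small sample without removing them.

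Much of this is fair. The label excuses the missing size calculation. It would be too strong to say that summaries are confined to background variables. What remains is the interval: step 4 shows that per-brush summaries do not supply it, and the exploratory clause permits it without committing to it.

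A reader might infer three further things that the documents do not support.

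- **That the p value alone will carry the conclusion.** The plan sets no rule for drawing a conclusion, so this cannot be read from it.
- **That a non-significant result is the likely outcome.** No SD or expected effect is given. The paired power runs from 29% to 80% over the differences shown, so the outcome depends on an unknown.
- **That the plan lacks a pooled tapered-versus-control estimate, (A+B)/2 - C.** Table 1 in section IV shows that C also differs in material (nylon against PBT) and in filament heights (13 and 13 mm against 10 and 13 mm), and that B's short filaments are rounded. The pooled contrast would mix taper with material and height, and would average two brushes that the objective sets out to compare. Its absence is not a fault.

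**Conclusion.** The point holds as an omission in the analysis plan: brush differences and their intervals are not planned, and the study is too small for a non-significant test to be informative without them. A 95% half-width of about 0.72 SD of the within-subject difference means that even an observed difference of zero would leave true differences of up to 0.72 SD in either direction plausible. The figures assume 10 completers, two-sided 5%, approximately normal differences and a paired analysis. With fewer completers the intervals widen. The widths are in units of the SD of the within-subject differences, so their clinical size cannot be judged from the documents.

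The use of a two-sample test on cross-over data is a related but separate weakness. Changing to paired tests would still leave the comparison without an estimate. The study can run without this change, but its conclusion would be weaker than its data allow, and the change is cheap.

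**What to change.** In section XVI, for both primary outcomes and for the secondary comparisons of plaque index, plaque area and gingival abrasion between brushes:

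- Make the main result the within-subject differences A-C, B-C and A-B, each with a 95% confidence interval.
- Take them from paired differences or from a model with subject, brush and period terms, and state in advance which.
- Where a rank method is used, report the median paired difference with its signed-rank interval.
- Base the proof-of-concept conclusion on these intervals, and state that a p value above 0.05 is not evidence of equal cleaning.

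Do not add a pooled contrast of A and B against C.

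The cost is a few sentences in section XVI and a few extra lines of output, with no new data, visits or subjects. The downside is that the intervals will be visibly wide.

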## **XII. STUDY PROCEDURE**

### **Screening and Enrollment Visit (Visit 1)**

Potential subjects will be instructed to refrain from regular oral hygiene regimen for 24 hours and eating for 4 hours before the appointment in the study.

Male and female subjects will read and sign the informed consent prior to enrollment. Subjects will be asked about demographics, medical history, general health status and current medication usage, and the information will be recorded.

Plaque Index (Quigley and Hein) of a whole mouth will be evaluated to verify that the subjects meet the inclusion and exclusion criteria (average PI>2).

If the participants meet the study criteria, they will be assigned to one of three treatment groups randomly based on computer generated randomized numbers.

Subjects will be instructed to use a toothpaste and a toothbrush (for wash-out period) provided by the study staff until the next visit. The appointment of next visit will be scheduled within 7 days ± one day.

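### The between-brush tests contain neither subject nor period, so any learning across visits stays in the error and, to a degree set by the realised sequence split, in the brush contrast

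*Combined protocol and SAP*

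**What the plan says.** Section VII describes an examiner-blinded cross-over with three cyclic sequences: A-B-C, B-C-A and C-A-B. "Subjects will be randomly assigned to one of three treatment groups", and Section XII (Visit 1) adds that they are "assigned to one of three treatment groups randomly based on computer generated randomized numbers". No block, quota or ratio is stated. On numbers, Section VI says "A total number of 10 subjects will be enrolled" and Section VII says that the study "will enroll subjects to target 10 subjects completing the study". Section XIV does not replace withdrawals.

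At the start of each product period, "subjects will receive a basic brushing instruction for Bass method by a study staff but without actual brushing". Table 2 schedules this instruction at Visits 2, 4 and 6. A supervised two-minute brushing follows, then a week of twice-daily home brushing by the taught method. Both primary outcomes (Section XV) are reductions from before to after that supervised brushing.

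Section XVI states that a Student t or rank sum test "will be used to compare among different bristles". It keeps the paired t and signed rank tests for change within a brush. No subject, sequence or period term appears. Section XV allows further exploratory analysis without specifying it.

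**The concern.** Every subject uses all three brushes, so the natural comparison is within subject, and it should allow for the order of use. The planned two-sample tests do neither.

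Order could matter here because the technique being taught acts on the endpoint. If subjects brush better at Visit 6 than at Visit 2, the reduction grows whichever brush is in hand. The same-visit pre-brushing score removes shifts in starting plaque, but not shifts in brushing skill.

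Two things are at stake. The first is precision: period shifts spread the brush differences even when the sequences are as balanced as ten subjects allow. The second is the contrast itself: ten does not divide by three, so part of any period shift remains in the raw brush means. Pairing the test recovers the between-subject variance but leaves both of these in place.

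**Working it through.** The documents give no SD, effect size, alpha or power, so there is no figure to reproduce. From the documents come the three sequences, 10 subjects and the named tests. Assumed are a linear gain of L per period (0, L, 2L), within-subject SD 1, between-subject SD 1, a true A-C difference of 1.4 and a two-sided 5% test.

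**Period shift in each contrast.** In Groups 1, 2 and 3, A-B is displaced by -1, +2, -1 steps, A-C by -2, +1, +1, and B-C by -1, -1, +2. With group sizes n1, n2, n3 and N = 10, the raw contrasts contain:
- A-C: L(N - 3·n1)/N
- A-B: L(3·n2 - N)/N
- B-C: L(3·n3 - N)/N

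At 4/3/3 these are -0.2L, -0.1L and -0.1L. At 5/3/2, A-C carries (10 - 15)/10 = -0.5L; at 6/2/2 it carries (10 - 18)/10 = -0.8L.

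**Period shift in the error at 4/3/3.** The residual mean square of a subject + brush model is 1 + 1.1L²: 1.275 at L = 0.5 and 2.10 at L = 1. The pooled variance of the unpaired test gains 0.19 and 0.77 respectively.

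**Subject term.** With L = 0 the unpaired test works with an SE of √(2 × (1 + 1)/10) = 0.632. The within-subject SE is √(2 × 1/10) = 0.447.

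**Cost of the period term.** There are 30 observations. Subject (10) and brush (2) leave 18 residual degrees of freedom; period takes 2, leaving 16. The SE of a contrast goes from 0.447 to 0.449 at 4/3/3, 0.464 at 5/3/2 and 0.488 at 6/2/2.

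**Simulated power for A-C at 4/3/3, four subjects in Group 1** (good to about one point):

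| Step L (SD) | Planned unpaired t | Subject + brush | Subject + brush + period |
|---|---|---|---|
| 0 | 58% | 84% | 83-84% |
| 0.25 | 53% | 80% | 83-84% |
| 0.5 | 45% | 70% | 83-84% |
| 1.0 | 25% | 38% | 83-84% |

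Placing the extra subject in Group 1 is the unfavourable 4/3/3 case for a true advantage of A, because the shift is -0.2L. With the extra subject in Group 2 or 3 it is +0.1L. The signal-to-error ratio for subject + brush at L = 0.5 is then (1.4 + 0.05)/(0.447 × √1.275) = 2.87, against (1.4 - 0.1)/(0.447 × √1.275) = 2.58. At L = 1 it is 1.5/(0.447 × √2.10) = 2.32 against 1.85. Simulated on the same assumptions (20,000 trials per case), subject + brush then has about 80% and 62% power at these steps, and the planned test about 57% and 48%. The loss is smaller, but in the same direction.

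**Which omission costs more.** In the table, at L = 0.5 the subject term is worth 70 - 45 = 25 points and the period term 13-14 more. At L = 1 the order reverses: 38 - 25 = 13 points, then about 45.

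**Sequence split, if allocation were simple.** P(4/3/3) = 3 × 10!/(4!·3!·3!)/3¹⁰ = 12,600/59,049 = 21%. The SD of the shift in one contrast is 3 × √(10 × 2/9)/10 = 0.447L, with mean zero.

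**False positives, if allocation were simple.** At L from 0 to 1, simulated null rejection for A-C is about 1-2.5% for the planned test and 4.5-6% for subject + brush.

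**The case against.** Several points on the other side stand.

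- **Learning is inferred.** No passage reports a period effect, and the design limits one. Instruction precedes every test brushing, including the first. Each test brushing is supervised and timed. Washout weeks return subjects to their usual habits. A step of 1.0 SD per period is an extreme. This limits the claimed size, not the case for the term.
- **Allocation.** A reader might infer that allocation is unrestricted. The documents do not say so: "randomly based on computer generated randomized numbers" is compatible with a blocked list. The 21% figure therefore holds only if allocation was simple.
- **Bias.** A reader might infer that the plan biases the brush comparison or inflates false positives in general. It does not. The shift depends on the realised split and averages zero over simple randomization, and the planned test is conservative overall. What remains is that this trial will have one split, which cannot be even.
- **The larger fault is elsewhere.** At small to moderate steps, leaving out the subject term costs more than leaving out period. This is accepted, and both terms should go in together.
- **Proof of concept.** Section XVI gives this as the reason for having no sample-size calculation. It does not explain tests that ignore a cross-over design, and changing them needs no extra subjects.

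**Conclusion.** The point holds. The between-brush tests in Section XVI ignore subject and period in a three-period cross-over where learning is plausible. At 4/3/3 any period shift inflates the error and moves a contrast by 0.1 to 0.2 step; a less even analysed split moves it further.

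On the stated assumptions, the full model holds power at 83-84% whatever the step. The planned t test starts at 58% with no learning and falls as the step grows, and pairing alone does not prevent the fall. The absence of both terms is read directly from the text. The power figures rest on assumed SDs, effect and step size, and on four subjects in Group 1. The documents do not establish a learning effect of any particular size, nor unrestricted allocation. It should be changed, as a cheap improvement rather than a fatal flaw.

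**What to change.** In Section XVI, replace the Student t and rank sum tests between brushes with a linear model containing subject, brush and period. Use it for every between-brush comparison, on the immediate and the one-week outcomes. In place of the rank sum test, specify a non-parametric sensitivity analysis that respects the within-subject pairing, such as the signed rank test on each subject's brush differences.

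The cost is wording, 2 of 18 residual degrees of freedom and, with no period effect at 4/3/3, about 1-2 points of power. The cost rises if the split is uneven: with no period effect at 6/2/2, simulated power drops from 85% to 77%.

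As a secondary clarification, state in Section XII (Visit 1) that the list is balanced over sequences (4/3/3). This limits the loss just described and the shift in raw means. It does not protect the analysed split, since withdrawals are not replaced, so it cannot stand in for the period term.
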